7.2 Institutional Review Board (IRB) Review

The protocol will be submitted to the IRB for review and approval. Approval of the protocol must be obtained before initiating any research activity. Any change to the protocol or study team will require an approved IRB amendment before implementation as well as appropriate submission to the FDA.

The IRB will conduct continuing review at intervals appropriate to the degree of risk, but not less than once per year. A study closure report will be submitted to the IRB after all research activities have been completed. Other study events (e.g. data breaches, protocol deviations) will be submitted per the IRB's policies.

7.3 Subject Confidentiality

Data collected in the course of the study will be de-identified and stored on REDCap and on a secure HIPAA-compliant central server within the Clinical and Translational Research

Accelerator. The server is only accessible from within the Yale intranet (or via VPN remotely) and additionally requires separate logon username and password. No PHI will be included in analysis or publication. All analyses will proceed on this server alone.

We will maintain a linking file in a separate location that will allow for future linking of de-identified data to protected health information (PHI) for the purpose of potential future studies. Studies that require the use of PHI (for example, linking patient info to national outcomes databases) will require approval the investigators.

7.4 Deviations/Unanticipated Problems

If the study team or monitor becomes aware of an unanticipated problem (e.g. data breach, protocol deviation), the event will be reported by the Investigator to the reviewing IRB according to their requirements and to the Sponsor within 10 business days. Within 10 business days of the receipt of this information, the Sponsor will notify in writing other reviewing IRBs, the study monitor (if not already involved), and the FDA in accordance with applicable regulations. Protocol deviations will be identified through the review of the CRFs and collected data by the Sponsor-Investigator after each subject is enrolled. The Sponsor-Investigator will also have a formal discussion with the study investigator after each case to assess for any potential protocol deviation. The study Monitor will also review each case and assess for protocol deviations.

7.5 Data Collection

- All participant data relating to the study will be recorded on printed or electronic CRF unless transmitted to the investigators electronically (e.g., laboratory data). The investigators are responsible for verifying that data entries are accurate and correct by physically or electronically signing the CRF.

Data will be obtained from the electronic health record via Yale's Joint Data Analytics Team (JDAT) as raw flat files from Clarity, the relational database from Epic. These files will then be transferred to our server via secure FTP. A deidentified dataset will be constructed by the study team using the Safe Harbor method of the HIPAA Privacy Rule, namely the removal of all 18 HIPAA identifiers.

Non PHI elements of this data pull will include the following (looking back a minimum of 10 years):

- Full patient medical history
- All available clinical care information during index encounter
- All available information from follow-up encounters following index hospitalization
- Provider type/class and location of treatment for all follow-up encounters following index hospitalization
- Patient coverage status
- The investigator must permit study-related monitoring, audits, IRB/IEC review, and regulatory agency inspections and provide direct access to source data documents.

- The investigators are responsible for the data management of this study including quality checking of the data.
- Records and documents, including signed ICFs, pertaining to the conduct of this study must be retained by the investigator for five years after study completion unless local regulations or institutional policies require a longer retention period.

7.6 Access to Source

- Source documents provide evidence for the existence of the participant and substantiate the integrity of the data collected. Source documents are filed at the investigator's site.
- Data reported on the CRF or entered in the eCRF that are transcribed from source documents must be consistent with the source documents or the discrepancies must be explained. The investigator may need to request previous medical records or transfer records, depending on the study. Also, current medical records must be available.
- The investigator must maintain accurate documentation (source data) that supports the information entered in the CRF.

Study monitors will perform ongoing source data verification to confirm that data entered into the CRF by authorized site personnel are accurate, complete, and verifiable from source documents; that the safety and rights of participants are being protected; and that the study is being conducted in accordance with the currently approved protocol and any other study agreements, ICH GCP, and all applicable regulatory requirements.

7.7 Data or Specimen Storage/Security

No specimens will be collected in the course of this study. Data Protection

- Participants will be assigned a unique identifier by the investigators.

7.8 Retention of Records

Records will be retained for at least 5 years after the end of the study.

7.9 Study Monitoring

The study will be monitored by the internal team as well as a dedicated external Data and Safety Monitoring Board.

The DSMB will meet at least twice a year to review data and will have a formal meeting to assess the interim analysis results.

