5.3.1 Number of Participants

We determined the overall sample size of this study based on the clinical composite outcome of progression of AKI, Dialysis, and Death. The baseline rate of this outcome is 21% based upon our preliminary data, and we felt that a relative 20% improvement (to 16.8%) would represent a clinically meaningful difference. In order to have 90% power to detect such a difference (or greater) if it exists at an alpha of 0.05, we would need to enroll 1,824 patients in each group, for a total of 3,648 in the study. Given concerns about contamination across the study arms (see III.J.9), we have increased this recruitment target by approximately 10% to a total of 4000 individuals. Enrollment of 4000 individuals will also allow us to detect a difference in the rate of adherence to recommendations of 10% of one standard deviation at an alpha of 0.05, which is ample power to determine if the provision of these recommendations change provider behavior.

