6.1.3 Method of Assignment/Randomization

Randomization will be performed within REDCap using a computer-generated randomization table which will use permuted blocks (of 4, 6 and 8 individuals). Randomization will be stratified by study hospital.

The Kidney Action Team will create recommendations for all patients that meet eligibility criteria, regardless of randomization status, which will preserve their blinding.

(Recommendations will only be delivered to patients in the intervention group). Providers and patients will not be blinded. Study investigators and analysts will be blinded to randomization status.

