6.4.2 Sample Size Considerations

We determined the overall sample size of this study based on the clinical composite outcome of progression of AKI, Dialysis, and Death. The baseline rate of this outcome is 21% based upon our preliminary data, and we felt that a relative 20% improvement (to 16.8%) would represent a clinically meaningful difference. In order to have 90% power to detect such a difference (or greater) at an alpha of 0.05, we would need to enroll 1,824 patients in each group, for a total of 3,648 in the study. Given concerns about contamination across the study arms (see III.L.9), we have increased this recruitment target by approximately 10% to a total of 4000 individuals. Table 2 shows a breakdown of recruitment by study site. Given the fact that this trial will operate under a waiver of informed consent, and our prior track record in this space, we expect full accrual across both sites within 3 years. Enrollment of 4000 individuals will also allow us to detect a difference in the rate of adherence to recommendations of 10% of one standard deviation at an alpha of 0.05, which is ample power to determine if the provision of these recommendations change provider behavior.

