6.4.3 Planned Analyses

6.4.3.1 Primary Analyses

The primary analysis will compare the proportion of patients experiencing the primary outcome (progression of AKI, Dialysis, or Death) at 14 days after randomization. We will compare the difference using the Cochrane-Mantel_Haenszel chi-square test, accounting for stratification by study hospital.

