6.4.3.2 Analysis of Subject Characteristics

We will compare the baseline characteristics of subjects in the two study groups using chi-square tests (for categorical variables) and Wilcoxon Rank Sum tests (for continuous variables).

7 - Trial Administration

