7.10 Data Safety Monitoring Plan

Data and Safety Monitoring Board

- Participant safety will be continuously monitored by the external DSMB, which includes safety signal detection at any time during the study
- Case unblinding may be performed for above reviews if necessary.

The DSMB may unblind the intervention assignment for any participant with an SAE. If the SAE requires that an expedited regulatory report be sent to one or more regulatory agencies, a copy of the report, identifying the participant's intervention assignment, may be sent to investigators in accordance with local regulations and/or sponsor policy.

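### Does the unspecified interim analysis in section 7.9 put the 0.05 error rate or the 90% power at risk?

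*Combined protocol and SAP*

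**What the plan says.** Section 7.9 (Study Monitoring) provides for an external board. Of its routine work it says "The DSMB will meet at least twice a year to review data", and then that the board "will have a formal meeting to assess the interim analysis results". That is the document's only mention of an interim analysis.

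Section 7.10 describes the board's task: "Participant safety will be continuously monitored by the external DSMB". It also allows assignments to be unblinded for individual serious adverse events. It contains no statistical stopping rule.

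Sections 5.3.1 and 6.4.2 set the sample size: "In order to have 90% power to detect such a difference (or greater) at an alpha of 0.05", for 21% against 16.8%, "we would need to enroll 1,824 patients in each group". The total of 3,648 is raised to 4,000 because of contamination between arms.

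Section 6.4.3.1 gives the primary test: "We will compare the difference using the Cochrane-Mantel_Haenszel chi-square test, accounting for stratification by study hospital". Section 6.4.3.2 adds a baseline comparison. Section 6.1.3 states "Study investigators and analysts will be blinded to randomization status".

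**The concern.** Section 7.9 speaks of the interim analysis as something already planned and gives it a meeting of its own. A reader who then turns to section 6.4.3 (Planned Analyses) finds only the primary and baseline comparisons. The sample size carries no allowance for an extra look, and the only significance level in the document sits in the sample size text.

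What is at stake depends on the unstated purpose:

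- A safety review affects neither error nor power.
- A futility stop keeps the type I error at or below 5% but can bring power under the stated 90%.
- An efficacy stop without a boundary raises the type I error above 5%.

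If the purpose were settled only after results by arm had been seen, a reader could not tell which of these applied. It is also not stated who would prepare results by arm while investigators and analysts are blinded.

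**Working it through.** **1. Reproduce the plan's figure.** Inputs from section 6.4.2: control rate 0.21, intervention rate 0.168, alpha 0.05, power 90%. Sidedness is not stated, so two-sided is tried first. The mean rate is (0.21 + 0.168)/2 = 0.189 and the difference is 0.042.

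n per group = [1.960·√(2·0.189·0.811) + 1.2816·√(0.21·0.79 + 0.168·0.832)]² / 0.042²

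= [1.960·0.5537 + 1.2816·0.5529]² / 0.001764 = (1.0852 + 0.7085)² / 0.001764 = 1,823.96

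This rounds up to the stated 1,824. A one-sided test would need 1,487, so two-sided 0.05 with a single final test is the design that was sized. The stated 90% power is therefore verified for that design.

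**2. Power at the enrolment target.** With 2,000 per group, z = (0.042·√2000 − 1.0852)/0.5529 = 1.434, so power is 92.4% and the drift is 1.434 + 1.960 = 3.39. At 1,824 per group the drift is 3.24. The rise from 3,648 to 4,000 (4,000/3,648 = 1.096) is assigned to contamination, so it should not be counted as spare power for an interim look. Both bases are shown below.

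**3. What each reading would do.** Everything here assumes one look; its number and timing are assumptions, because the document gives neither. The interim and final statistics are taken as bivariate normal with correlation √f, where f is the information fraction at the look.

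| Assumed use of the look | Type I error | Power, 1,824 per group | Power, 2,000 per group |
|---|---|---|---|
| Safety only | 5.0% | 90.0% | 92.4% |
| Futility, f = 0.5, stop if interim z < 0 | at most 5% | 89.8% | 92.2% |
| Futility, f = 0.5, stop if z < 0.745 (current-trend conditional power below 10%) | at most 5% | 87.3% | 90.0% |
| Futility, f = 0.5, stop if z < 0.965 (below 20%) | at most 5% | 85.3% | 88.2% |

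Power figures are before any dilution by contamination. For the three futility rules the upper-tail error is 0.0247, 0.0222 and 0.0205, against 0.025 without a stop.

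For an efficacy claim, the error is 1 − P(|Z₁| < c₁, |Z₂| < 1.96):

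- Unadjusted, c₁ = 1.96: 9.1%, 8.3% and 7.3% at f = 0.25, 0.5 and 0.75.
- Strict interim threshold p < 0.001, f = 0.5, final test left at 0.05: 5.02%.
- Lan-DeMets O'Brien-Fleming interim (z = 2.963, p < 0.0031), f = 0.5, final test left at 0.05: 5.10%.
- The same boundary with the final level adjusted to 0.0490: 5.0%, with power at 2,000 per group of 92.35% against 92.43% for the single-test design.

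**4. Which reading the text supports.** The sentence stands in a section on monitoring. In it the word formal describes the board's meeting, not the analysis. The section that follows words the board's task as participant safety. No section mentions stopping for efficacy or futility, or testing the primary outcome before the end. The absence from section 6.4.3 says little, because that section is not a full list: the Van Elteren comparison of adherence appears only in 6.4.1, and the secondary outcomes and the assessment across sites only in 5.2.2. The stronger observation is that no rule appears anywhere, and a rule that does not exist gives an analyst nothing to apply before the final test.

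**The case for a change.** The best case for acting is that section 7.9 lists the interim results in addition to the routine data reviews and never calls them safety results. No DSMB charter is cited. Some plausible rules would matter: a futility stop at conditional power below 20% brings power under 90% even with 4,000 patients and no contamination. A paragraph settling the purpose would need no extra patients, and an O'Brien-Fleming-type boundary at half the information would lower power by only about 0.1 point.

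Much of this stands. The interim is undescribed, and a reader cannot work out the error and power of a trial run with an interim rule of unknown form. But that shows an unstated detail, not an inflated error. The 7.3–9.1% range needs an efficacy claim at an unadjusted 0.05, which no section provides for, and the power losses need a futility rule that is equally absent. The document also cites material that is not in it (sections III.J.9 and III.L.9, and Table 2), so one can say that the details are not given here, but not that they were never fixed. Who prepares reports by arm is an operational matter for the board and does not alter the primary test.

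**Conclusion.** The omission is genuine but leads to no change in the plan. As written, the plan has one final Cochran-Mantel-Haenszel test stratified by hospital, sized at two-sided 0.05, with a board that reviews safety. An analyst who follows it gets a valid result: error 5.0%, power 90.0% at 1,824 per group and 92.4% at 2,000 before contamination. Asking for more would only ask the sponsor to write down whichever purpose it already has, with a boundary needed only if an efficacy stop is meant.

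The conclusion rests on two assumptions: that the test is two-sided, as the exact match at 1,824 implies, and that the interim is for safety, as section 7.10 suggests but section 7.9 does not say. If the board were in fact to stop for efficacy or futility, the second would fail and the figures above would show the size: at half the information, error from 5.02% to 8.3% for the efficacy cases with the final test left at 0.05, or power down to 85.3% at 1,824 per group for the strictest futility rule tried.

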7.10 Data Safety Monitoring Plan

Data and Safety Monitoring Board

- Participant safety will be continuously monitored by the external DSMB, which includes safety signal detection at any time during the study
- Case unblinding may be performed for above reviews if necessary.

The DSMB may unblind the intervention assignment for any participant with an SAE. If the SAE requires that an expedited regulatory report be sent to one or more regulatory agencies, a copy of the report, identifying the participant's intervention assignment, may be sent to investigators in accordance with local regulations and/or sponsor policy.

7.11 Study Modification

Study modifications will be implemented upon approval from the IRB.

7.12 Funding Source

This study is funded by a grant from the Association of Healthcare Research and Quality.

Appendix 1: Kidney Action Team Note Template**Kidney Action Team Recommendation Note**

Date: Time:

The Kidney Action Team is a group of clinicians designed to provide personalized recommendations for the diagnosis and treatment of patients with Acute Kidney Injury (AKI).

We have been notified that this patient has developed AKI within the past hour. We have reviewed the patient's chart and, based on the patient's current status and medical history, make the specific recommendations listed below.

*****For all AKI patients, we recommend continued follow-up of serum creatinine and avoiding nephrotoxic exposures.*****

KIDNEY ACTION TEAM PERSONALIZED RECOMMENDATIONS FOR YOUR AKI PATIENT:

- ❖ Obtain urinalysis (if not already obtained)
- ❖ Avoid new nephrotoxic exposures
- ❖ Follow creatinine at least every 24 hours
- ❖ Rule out obstruction via PVR or ultrasound
- ❖ Provide bicarbonate supplementation
- ❖ Stop PPI
- ❖ Consider Renal Consult

Please note: This patient is part of a randomized clinical trial designed to test the efficacy of personalized recommendations for the diagnosis and treatment of Acute Kidney Injury. You will NOT receive this recommendation note for all patients who develop AKI.

The Kidney Action Team has not seen or examined this patient. Our recommendations are based on chart review only. **It is your choice to follow these recommendations using your own clinical judgement and your examination of the patient and his/her medical history.** Should you choose to follow any of the recommendations, the Kidney Action Team will not follow up on test results or provide any further recommendations. *If you need assistance with AKI management, please consider a formal kidney consult. Medication recommendations are based on currently prescribed medications. Please reach out to your floor pharmacist if any further questions about starting renally cleared medications.*

Please cosign to acknowledge receipt of the recommendations.

Signed By:

Date:
